	Visit	D1	D15	w12	D1	w12	D1	w12	D1	w12				
Week in OLE Phase (window in days)	0 (±5)	2 (±5)	12 (±7)	24 (±5)	36 (±7)	48 (±5)	60 (±7)	72 (±5)	84 (±7)	n (±5)	n+12w (±7)			
	U	U		U		U		U		U				
Informed consent ^f	x													
Review of eligibility criteria	x													
Review of re-treatment criteria	x	x		x		x		x		x		x		
Physical examination	x	x		x		x		x		x		x	x	x
Vital signs ^g	x	x	x	x	x	x	x	x	x	x	x	x	x	x
12 lead ECG ^h	x					x				(x)				x
Weight (annually)						x				(x)				x
Neurological examination	x	x	x	x	x	x	x	x	x	x	x	x	x	x
EDSS, and MSFCS	x		x	x	x	x	x	x	x	x	x	x	x	x
Adverse events	x	x	x	x	x	x	x	x	x	x	x	x	x	x
Potential relapses recorded	x	x	x	x	x	x	x	x	x	x	x	x	x	x
MFIS, SF-36 (once annually)	x				x		x		x		(x)			x
Telephone interview ⁱ	x	x	x	x	x	x	x	x	x	x	x	x		x
Concomitant treatment	x	x	x	x	x	x	x	x	x	x	x	x	x	x
MRI ^j (once per year)	x					x				(x)				x
Pregnancy test ^k	x	x	x	x	x	x	x	x	x	x	x	x	x	x
Antibody titers ^l	x		x		x		x		x		x			x

Table 4 Schedule of Activities: Open-Label Extension Phase (cont.)

Cycle	OLE Phase ^{a, b}											Delayed Dosing Visit ^d	Unscheduled Visit ^e	Withdrawal from Treatment Visit
	1			2		3		4		N ^c				
	D1	D15	w12	D1	w12	D1	w12	D1	w12					
Week in OLE Phase (window in days)	0 (±5)	2 (±5)	12 (±7)	24 (±5)	36 (±7)	48 (±5)	60 (±7)	72 (±5)	84 (±7)	n (±5)	n+12w (±7)			
	↓	↓		↓		↓		↓		↓				
HAHA ^m						x								
PK samples ^m						x								
HBV DNA ⁿ	x		(x)	(x)	(x)	(x)	(x)	(x)	(x)	(x)	(x)			(x)
CD4 count			x		x		x		x		x			x
Total Ig, IgA, IgG, IgM	x		x		x		x		x		x			x
FACS ^o	x			x		x		x		x				x
Routine safety laboratory tests ^p	x		x		x		x		x		x			x
RCR (Protein) ^q	x			x		x		x		x				x
Open-label clinical genotyping ^r	x		(x)	(x)	(x)	(x)	(x)	(x)	(x)	(x)	(x)			(x)
Pretreatment with IV methylprednisolone and antihistamine ^s	x	x		x		x		x		x		x		
Administration of IV ocrelizumab ^t	x	x		x		x		x		x		x		
Optional samples for RBR (CSF and blood) ^u						x								

Table 4 Schedule of Activities: Open-Label Extension Phase (cont.)

β -hCG = β human chorionic gonadotropin; CD = cluster of differentiation; CSF = cerebrospinal fluid; D = Day; eCRF = electronic Case Report Form; EDSS = Expanded Disability Status Scale; FACS = fluorescence-activated cell sorting; Fc = fragment crystallizable; HAHA = human anti-human antibody; HBcAb = hepatitis B core antibody; HBsAg = hepatitis B surface antigen; HBV = hepatitis B virus; MFIS = Modified Fatigue Impact Scale; MRI = magnetic resonance imaging; MS = multiple sclerosis; MSFCS = Multiple Sclerosis Functional Composite Scale; OLE = open-label extension; PCR = polymerase chain reaction; PK = pharmacokinetic; RBR = Research Biosample Repository; RCR = Roche Clinical Repository; SF-36 = Short Form-36; w = week.

- ^a **OLE phase cycles:** The OLE phase will start after the primary analysis and communication from the Sponsor. The OLE phase can terminate at any moment or cycle (see Section 4.1.9). In case the study is ended, a Withdrawal from Treatment Visit should occur *for any participants not rolling over to Study MN43964*.
- ^b All participants entering the OLE will receive a dual ocrelizumab infusion (300 mg IV infusions administered 14 days apart) for the first cycle. For the subsequent cycles, participants will continue open-label treatment with a single infusion of 600 mg ocrelizumab IV every 24 weeks.
- ^c The assessments requested for N represent the typical schedule of activities during a cycle.
- ^d A **delayed dosing visit** will be performed and recorded in the Delayed Dosing Visit eCRF when dosing cannot be administered at the scheduled dosing visit. Other tests/assessments may be done as appropriate.
- ^e **Unscheduled Visit (non-dosing):** Assessments performed at unscheduled (non-dosing) visits will depend on the clinical needs of the participant. All participants with new neurological symptoms suggestive of MS worsening or of a relapse should have EDSS performed by Examining Investigator. Other tests/assessments may be done as appropriate.
- ^f **Informed Consent** for OLE must be signed by the participant prior to the first infusion in the OLE phase.
- ^g **Vital signs** will be obtained while the participant is in the semi-supine position (after 5 minutes), including pulse rate, systolic and diastolic blood pressure, respiration rate, and temperature. At infusion visits, the vital signs for all participants should be taken within 45 minutes prior to the methylprednisolone infusion. In addition, vital signs should be obtained prior to the study drug or placebo infusion, then every 15 minutes (± 5 minutes) for the first hour; then every 30 minutes (± 10 minutes) until 1 hour after the end of the infusion. At non-infusion visits, the vital signs may be taken at any time during the visit.
- ^h **ECGs (pre- and postdose):** ECG should be performed within 45 minutes prior to the methylprednisolone infusion in all participants and within 60 minutes after completion of the ocrelizumab infusion. From OLE Week 72 onwards, ECG assessment is not mandatory; it should only be performed if clinically indicated.
- ⁱ **Telephone interview:** A structured **telephone interview** will be conducted by site personnel every 4 weeks *between visits* to identify and collect information on any changes in the participant's health status that warrant an unscheduled visit (including new or worsening neurological symptoms).
- ^j **MRI scans:** A brain MRI scan should be performed at the start of OLE phase if not done in the previous 12 weeks. In the OLE phase, brain MRIs should be done once a year. Brain MRI scans should occur within a window of ± 4 weeks of the scheduled visit. Also, brain MRI scans will be obtained in participants withdrawn from the OLE phase (at a withdrawal visit) if not performed during the previous 4 weeks.

- ^k **Antibody titers:** Measurement of antibody titers against common antigens (mumps, rubella, varicella, and *S. pneumoniae*) will be performed.
- ^l **HAHA:** In any case of anaphylaxis, anaphylactoid reaction, or serious or severe hypersensitivity reaction, HAHA and ocrelizumab concentration samples should be collected as close as possible to the event and then at 4 and 16 weeks postdose.
- PK samples:** In any case of anaphylaxis, anaphylactoid reaction, or serious or severe hypersensitivity reaction, HAHA and ocrelizumab concentration samples should be collected as close as possible to the event and then at 4 and 16 weeks postdose.
- ^m **Hepatitis monitoring:** For those participants enrolled with negative HBsAg and positive total HBcAb, HBV DNA (PCR) must continue to be repeated every 12 weeks during the OLE phase.
- ⁿ **FACS:** Including CD19 and other circulating B cell subsets, T cells, natural killer cells and other leukocytes. FACS samples should be collected prior to infusion. See Section 5.13.2 for specific tests.
- ^o **Routine safety laboratory tests:** Hematology, chemistry, and urinalysis: On the infusion visit (Cycle 1, Day 1), urine and blood samples should be collected prior to the infusion of methylprednisolone. At all other times, samples may be taken at any time during the visit. Samples collected during unscheduled visits should preferably be sent to and analyzed by the central laboratory and not local unless results are required urgently.
- ^p **RCR (Protein)** 6 mL blood samples in EDTA tube for plasma will be taken from consenting participants for analysis of protein biomarkers. Samples should be collected 5–30 minutes prior to methylprednisolone infusion.
- ^q **Open-label clinical genotyping:** A 3 mL whole blood sample will be taken one time from participants that did not have a sample collected for DNA analysis of HLA-DR and Fc γ polymorphisms during the blinded treatment period. If not collected at the first OLE phase visit (Visit 1), the sample may be collected at any subsequent visit.
- ^r All participants will receive **prophylactic treatment** with 100 mg of methylprednisolone IV and an oral or IV antihistamine, such as diphenhydramine 50 mg or equivalent dose of alternative, prior to infusion with ocrelizumab. *The methylprednisolone administration is to be completed approximately 30 minutes before the start of each ocrelizumab infusion; antihistamines should be administered 30–60 minutes prior to the start of an infusion.* In the rare case when the use of methylprednisolone is contraindicated for the participant, use of an equivalent dose of an alternative steroid (e.g., dexamethasone) should be used as premedication prior to the infusion. It is also recommended that participants receive an analgesic/antipyretic such as acetaminophen/paracetamol (1 g) 30–60 minutes prior to ocrelizumab infusions.
- ^s **Study drug administration:** The Treating Investigator must review the clinical and laboratory re-treatment criteria prior to re-dosing participants with study drug in all subsequent treatment cycles. The participant will need to remain under observation at the clinic for at least 1 hour after infusion. It is anticipated that the participant will need to stay at the hospital or clinic for a full day for the infusion visit.
- ^t One-time optional CSF, paired plasma samples, and blood samples for the RBR collected at any timepoint in the OLE phase. These samples should be collected after the participant's consent and at the next possible visit during the OLE phase.

PART I: STUDY DESIGN AND CONDUCT

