- ^a **Additional treatment cycles:** Participants will continue with blinded 24-week treatment cycles until the last participant receives his/her final course of treatment scheduled at Week 98. At that point, all participants will continue to the end of their current (24-week) cycle. If the projected total number of confirmed disability progression events has not been reached at Week 120, then all participants will continue with additional blinded 24-week treatment cycles until the projected number of confirmed disability events has been reached.
- ^b Participants undergoing the first infusion of the first additional treatment cycle at Week 120 should also complete all assessments for the Week 120 visit outlined in [Table 1](#).
- ^c A **delayed dosing visit** will be performed and recorded in the Delayed Dosing Visit eCRF when dosing cannot be administered at the scheduled dosing visit. Other tests/assessments may be done as appropriate.
- ^d **Unscheduled Visit** (non-dosing): Assessments performed at unscheduled (non-dosing) visits will depend on the clinical needs of the participant. All participants with new neurological symptoms suggestive of MS worsening or of a relapse should have EDSS performed by Examining Investigator. Other tests/assessments may be done as appropriate. Unscheduled visits may also take place during the safety follow-up period.
- ^e **Vital signs** will be obtained while the participant is in the semi-supine position (after 5 minutes), i.e., pulse rate, systolic and diastolic blood pressure, respiration rate and temperature. On infusion visits, the vital signs should be taken within 45 minutes prior to the methylprednisolone infusion in all participants. In addition, vital signs should be obtained prior to the study drug or placebo infusion, then every 15 minutes (± 5 minutes) for the first hour; then every 30 minutes (± 10 minutes) until 1 hour after the end of the infusion. On non-infusion days, the vital signs may be taken at any time during the visit.
- ^f A structured **telephone interview** will be done on a 4-week basis between visits *up to* 48 weeks after the last infusion to identify and collect information on any changes in the participant's health status (including, new or worsening neurological symptoms that warrant an unscheduled visit. For OLE, telephone interviews will be done on a 4-week basis for the first year and every 8-weeks subsequently.

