5.10.1.3 Visits During the Open-Label Extension Phase

Participants enrolled in the OLE phase will receive a dual ocrelizumab infusion (300 mg IV infusions administered 14 days apart) for the first cycle. For the subsequent cycles, participants will continue open-label treatment with a single infusion of 600 mg ocrelizumab IV every 24 weeks. See [Table 4](#) for detailed information on the assessments that will be performed during the OLE phase. All participants participating in OLE phase must continue to be eligible for re-dosing as outlined in the criteria for re-treatment with ocrelizumab (Section 6.2.3).

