5.12.4.1 Telephone Interview for New/Worsening Neurological Symptoms

The purpose of this structured interview is to identify and collect information on any changes in the participant's health status (including new or worsening neurological symptoms) that warrant an unscheduled visit. The telephone interview will be conducted by site personnel familiar with the participant(s) every 4 weeks between the study visits during the blinded treatment period, OLE phase, and throughout the safety follow-up period.

The site will record the date of the telephone interview in the eCRF and documentation of the interview will be maintained in the participant's Study File.

See [Appendix 5](#) for detailed information.

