7.3.4.1 Guidance for Diagnosis of PML

The following diagnostic algorithm framework (see [Figure 1](#)) will be implemented in this study.

Comprehensive neurological assessments will be performed every 12 weeks at the regular study visits. Participants will be required to undergo a neurological examination for calculation of an EDSS score every 12 weeks. This requires that FSS also be determined. The examination to calculate the FSS includes cognitive, visual and motor assessments, the neurological systems most often affected by PML, as well as assessments of other neurological systems.

In the eCRF, the investigator will record the presence or absence of neurological deficits localized to the cerebral cortex (e.g., cortical symptoms/signs, behavioral and neuropsychological alteration, retrochiasmal visual defects, hemiparesis), cerebellar symptoms/signs (e.g., gait abnormalities, limb incoordination), at each visit. Presence of such neurological findings will be recorded as adverse events.

If a diagnosis for the deficits is identified, the symptoms should be replaced by the diagnosis in the adverse event eCRF.

In addition to the neurological evaluation at regular visits, participants will undergo a telephone interview between the study visits by site personnel familiar with the participant(s). The purpose of this interview is to identify new or worsening neurological symptoms that warrant an unscheduled visit ([Appendix 5](#)). Partners or caregivers of study participants, if applicable, will be informed on symptoms and signs that may be suggestive of PML and should be instructed to contact the site, should any such signs or symptoms appear.

In the event that new or worsening neurological symptoms are considered during the telephone interview, a neurological evaluation will be conducted. Should a non-MS etiology, such as PML, be considered, further assessments should be done (see [Figure 1](#)).

The following clinical guidance is provided.

Treatment of Relapse and Other Neurological Symptoms

- As in all MS studies, new or recurrent neurological symptoms occurring in study participants should prompt careful clinical evaluation
- Given the occurrence of PML in immunocompromised participants with other anti-CD20 and MS DMTs, PML should be considered in participants who develop worsening neurological signs or symptoms

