Appendix 5 Telephone Interview

The purpose of this interview is to identify and collect information on any changes in the participant's health status (including new or worsening neurological symptoms) that warrant an unscheduled visit.

The telephone interview will be conducted by site personnel familiar with the participant(s) every 4 weeks between the study visits.

The date of the telephone interview will be recorded in the eCRF.

The use of this form is optional, but if not used, all information should be recorded in the participant's medical records. Where used, this form should be kept with the participant's records.

Please ask the following questions during the telephone interview:

Read aloud and record participant's answers to the following questions:

Questions	No	Yes
1. Since your last visit or telephone interview, have you had any new or worsening medical problems (such as sudden changes in your thinking, alterations in your behavior, visual disturbances, extremity weakness, limb coordination problems, or gait abnormalities) that have persisted more than 1 day?		
2. Since your last visit or telephone interview, have you had any signs of an infection?		
3. Since your last visit or telephone interview, have you had any other new or worsening medical problems or conditions (including pregnancy or pregnancy of the partner of a male participant), surgery, or hospitalization?		
4. Since your last visit or telephone interview, have you taken any new medicines (including medicines to treat cancer or MS, any other new medicines that weaken your immune system, or steroid medicines other than for the treatment of a recent relapse)?		

If the participant answered YES to any question, contact the investigator and review the participant's answers. The investigator can determine if an unscheduled visit is required.

Record any pertinent comments made by the participant during the interview:

Name and date of staff completing the telephone interview:

NAME: _____ Date: _____

Below is a sample list of medications that can weaken the immune system:

Examples of Immunosuppressants, Antineoplastics, and Immunomodulators

Approved MS Therapies (approved in at least 1 country):

- Glatiramer acetate (Copaxone®)
- Interferon beta-1a (Rebif®, AVONEX®)
- Interferon beta-1b (Betaseron®)
- Mitoxantrone (Novantrone®)
- Natalizumab (Tysabri®)
- Fingolimod (Gilenya®)
- Alemtuzumab (Lemtrada®)
- Teriflunomide (Aubagio®)
- Dimethyl fumarate (Tecfidera®)

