The screening period may be extended (but cannot exceed 8 weeks) for participants who have used systemic corticosteroids for their MS before screening. For a participant to be eligible, systemic corticosteroids should not have been administered also between screening and baseline.

SCHEDULE OF ACTIVITIES AND PROCEDURES

Schedule of activities in this substudy will be identical to that of participants entering OLE through the main protocol (Table 4 of Section 1.2 of main protocol), with the exception of screening period that is inserted specifically for this substudy before the OLE treatment phase.

See Table 1 for the schedule of activities for screening period, OLE treatment phase, delayed dosing visit, Unscheduled visit, and Withdrawal from Treatment Visit.

For the safety follow-up period, the same provisions apply as for the participants entering OLE through the main protocol. See Table 3 of Section 1.2 of the main protocol for schedule of activities during safety follow-up period.

Appendix 8 Open-Label Extension Substudy in Participants Who Discontinued Treatment in the Blinded Phase of Study WA25046 (Cont.)

Table A8-1 Substudy Schedule of Activities

Cycle Visit	Unique To Substudy	Substudy Open-Label Treatment Phase (Identical To Main Study OLE) ^{a, b}							Delayed Dosing Visit ^d	Unscheduled Visit ^e	Withdrawal from Treatment Visit
		1			2		N ^c				
		D1	D15	w12	D1	w12					
Week in OLE Phase (window in days)	Screening -28 to -1	0 (±5)	2 (±5)	12 (±7)	24 (±5)	36 (±7)	n (±5)	n + 12 wk (±7)			
		U C	U C		U C		U C				
Informed consent ^f	x				Same as main study OLE schedule	Same as main study OLE schedule	Same as main study OLE schedule	Same as main study OLE schedule	Same as main study OLE schedule	Same as main study OLE schedule	Same as main study OLE schedule
Medical history ^g	x										
Review inclusion/exclusion criteria	x										
Review of re-treatment criteria		x	x								
Physical examination	x	x	x								
Vital signs ^h	x	x	x	x							
12 lead ECG ⁱ		x									
Weight	x										
Neurological examination	x	x	x	x							
EDSS, and MSFCS	x	x		x							
Adverse events	Only SAEs	x	x	x							
Potential relapses recorded ^j	x	x	x	x							
MFIS, SF-36, EQ-5D (once annually)		x									
Telephone interview ^k		x	x	x							
Concomitant treatment		x	x	x							

**Appendix 8 Open-Label Extension Substudy in Participants Who Discontinued Treatment in the Blinded Phase of Study WA25046
(cont.)**

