- ^h **Vital signs** will be obtained while the participant is in the semi-supine position (after 5 minutes), including pulse rate, systolic and diastolic blood pressure, respiration rate, and temperature. At infusion visits, the vital signs for all participants should be taken within 45 minutes prior to the methylprednisolone infusion. In addition, vital signs should be obtained prior to the study drug or placebo infusion, then every 15 minutes (± 5 minutes) for the first hour; then every 30 minutes (± 10 minutes) until 1 hour after the end of the infusion. At non-infusion visits, the vital signs may be taken at any time during the visit.
- ⁱ **ECGs (pre- and postdose)**: ECGs should be performed within 45 minutes prior to the methylprednisolone infusion in all participants and within 60 minutes after completion of the ocrelizumab infusion. From Week 72 onwards, ECG assessment is not mandatory; it should only be performed if clinically indicated.
- ^j Any clinical **relapses** from the time of discontinuation from the main study need to be reported.
- ^k A structured **telephone interview** will be conducted by site personnel every 4 weeks to identify and collect information on any changes in the participant's health status that warrant an unscheduled visit (including new or worsening neurological symptoms).
- ^l **MRI scans**: a brain MRI scan should be performed at the start of the substudy. Brain MRIs should be done once a year. Brain MRI scans should occur within a window of ± 4 weeks of the scheduled visit. Also, brain MRI scans will be obtained in participants withdrawn from the substudy (at a withdrawal visit) if not performed during the previous 4 weeks.
- ^m **Urine β -hCG** (sensitivity of at least 25 mIU/mL) will be performed. On infusion visits, the urine pregnancy test should be performed prior to methylprednisolone infusion in all women of childbearing potential. If positive, the participant will not receive the scheduled dose, and for confirmation, a serum pregnancy test will be performed.
- ⁿ **Antibody titers**: measurement of antibody titers against common antigens (mumps, rubella, varicella, and *S. pneumoniae*) will be performed.
- ^o **HAHA**: on infusion visits, samples are collected prior to the methylprednisolone infusion.

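### A footnote in the blinded-cycle schedule moves open-label telephone interviews to every 8 weeks after year 1, against every 4 weeks everywhere else in the protocol

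*Protocol*

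**What the plan says.** Table 2 in Protocol Section 1.2 covers extra blinded treatment cycles and some related visit types. Its telephone interview row is labelled as 4-weekly. Footnote f to that row ends with a rule for a different phase: "For OLE, telephone interviews will be done on a 4-week basis for the first year and every 8-weeks subsequently".

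Four other places in the protocol give an interval that applies to the OLE or to all phases:

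- **Table 4 footnote i** (the OLE schedule): the interview "will be conducted by site personnel every 4 weeks", between visits.
- **Section 5.12.4.1**: "every 4 weeks between the study visits during the blinded treatment period, OLE phase, and throughout the safety follow-up period".
- **Appendix 5** (the interview form): "The telephone interview will be conducted by site personnel familiar with the participant(s) every 4 weeks between the study visits".
- **Appendix 8, Table A8-1 footnote k** (the OLE substudy): the interview "will be conducted by site personnel every 4 weeks to identify and collect information".

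Section 5.10.1.3 points to Table 4 "for detailed information on the assessments that will be performed during the OLE phase", and Sections 4.1.3 and 5.23.1 do likewise.

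**The concern.** Footnote f is current text and is worded as a rule, so the protocol contains two incompatible instructions for the same procedure from the second OLE year onward. A site calling every 8 weeks would comply with Table 2 and deviate from Table 4. SAP Section 4.3 plans a summary of protocol deviations, which needs a single rule to be coded consistently.

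The call has a safety function. Section 7.3.4.1 makes it part of the PML diagnostic framework and says: "The purpose of this interview is to identify new or worsening neurological symptoms that warrant an unscheduled visit". Table 10 describes PML as progressing over weeks, so a difference between 4 and 8 weeks is relevant. The form in Appendix 5 also asks about infection, pregnancy and new medicines. The independent data monitoring committee is no longer involved during the OLE (Section 10.2), which leaves more of the monitoring to site contacts.

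For early entrants the affected period is most of the phase. SAP Section 1 dates OLE access from 12 October 2015, and Protocol Section 4.1.3 ends treatment by 31 December 2022.

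**Working it through.** No sample size, power, event count or significance level enters this point, and the plan states no figure to reproduce. The check compares the texts and then counts calls.

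**Step 1. The texts side by side.**

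| Place | Scope | Interval after OLE year 1 |
|---|---|---|
| Table 2 footnote f, last sentence | OLE, stated in a blinded-cycle table | every 8 weeks |
| Table 4 footnote i | OLE schedule | every 4 weeks |
| Section 5.12.4.1 | blinded period, OLE and safety follow-up, all named | every 4 weeks |
| Appendix 5 | general, no exception by phase | every 4 weeks |
| Table A8-1 footnote k | OLE substudy | every 4 weeks |

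These sources do not carry equal weight. Table 4 and Section 5.12.4.1 conflict with footnote f directly. Appendix 5 conflicts only because it makes no exception for the OLE. Appendix 8 says "Schedule of activities in this substudy will be identical to that of participants entering OLE through the main protocol" (screening apart), so it follows Table 4 and is not independent evidence. Even on the narrowest count, two direct statements oppose footnote f and none supports it.

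**Step 2. Which interval was meant.** The amendment rationale says that substantive new information is set in italics. In Table 4 footnote i the qualifier about calls falling between visits is italic, so that sentence was edited in this version and the 4-week interval was kept. Footnote f was also edited (an italic change elsewhere in it), but its OLE sentence was left alone. This favours 4 weeks, although the documents do not state the intent.

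**Step 3. Size.** Take 48 OLE weeks after year 1. Visits are 12 weeks apart (Table 4), at weeks 0, 12, 24, 36 and 48. Count only calls that do not fall on a visit.

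- *Every 4 weeks:* weeks 4, 8, 16, 20, 28, 32, 40, 44. That is 8 calls, or 8 / 4 intervals = 2 per interval. The longest gap between contacts is 4 weeks.
- *Every 8 weeks on a continuous grid:* weeks 8, 16, 32, 40 (weeks 24 and 48 coincide with visits). That is 4 calls, or an average of 4 / 4 = 1 per interval. The longest gap is 8 weeks, for example from the week 24 visit to the week 32 call.
- *Every 8 weeks counted from each visit:* weeks 8, 20, 32, 44. That is again 4 calls, with a longest gap of 8 weeks.

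Both readings of the 8-week rule halve the number of calls (4 / 8 = 0.5) and double the longest gap (8 / 4 = 2).

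**The case against.** The strongest reply is that Table 2 does not govern the OLE. Section 4.1.3 applies it only until the primary analysis is complete and the OLE starts. OLE sites, including those handling OLE withdrawals, are sent to Table 4, which already has the 4-week rule. The blinded period was unblinded in September 2015, so a site working from the current version had no blinded cycles left to run from Table 2. On this view the sentence is a stray remark that nobody would follow. This stands as a reason for a low grade. It does not remove the conflict, because the sentence expressly addresses the OLE and sets an interval for it.

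A second reply is that so specific a step-down may have been a deliberate reduction in burden that was never carried through. That cannot be excluded. Nothing else in the protocol reflects it, however, and the governing OLE footnote was revised without it.

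A third is that the safety consequence is thin. Neurological assessment stays 12-weekly, caregivers are told which PML signs to report (Section 7.3.4.1), and symptomatic participants are to be seen promptly whatever the visit schedule (Section 5.23.3). All of that stands, and no measure of lost detection can be given from the documents.

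Finally, with closure set for 31 December 2022 and the SAP dated March 2023, a correction has little effect on conduct. That is fair. What remains is a consistent protocol and consistent handling of deviations.

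**Conclusion.** The inconsistency is real and minor. Table 2 footnote f is the only text that sets an 8-week interval. It contradicts the OLE schedule and Section 5.12.4.1 directly, and Appendices 5 and 8 by extension. If followed, it would halve the calls between visits after OLE year 1, from 8 to 4 per 48 weeks, and lengthen the longest gap between scheduled contacts from 4 to 8 weeks.

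The count assumes visits held exactly 12 weeks apart, without visit windows, and every scheduled call made. The documents do not show that any site used 8 weeks, or how long the footnote has read this way. Adverse events are reported at each visit (Section 7.1.1), and the visit schedule does not change. The primary endpoint, the blinded-period analyses and the sample size are untouched.

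**What to change.** Keep the 4-week interval. Delete the last sentence of Table 2 footnote f, or change it to every 4 weeks, so that it agrees with Table 4 footnote i, Section 5.12.4.1, Appendix 5 and Table A8-1 footnote k. Send sites a short note. If the sponsor did intend 8 weeks, those four other places would have to change instead, with a stated reason.

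Section 5.12.4.1 has interview dates recorded in the electronic case report form, so the sponsor can also check which interval sites used and classify any deviations against the 4-week rule.

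The cost is one deleted sentence and a short notice.
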